### 5.3 Safety Evaluation

Adverse events (AEs), whether anticipated or unanticipated, will be recorded according to the date of first occurrence, severity, and their duration. Notably, ARDS is a life-threatening condition for which we expect a wide range of events as part of the routine clinical course. Secondary Safety Endpoints include: pneumothorax requiring chest tube; acidosis requiring additional vasopressor support; protocol termination for failure criteria; other air leak not requiring chest tubes. Ventilator-

associated pneumonia; new or progressive multiple organ dysfunction syndrome are being recorded as secondary aims, and also serve as potential safety outcomes.

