## 8.6 Investigator Reporting of a Serious Adverse Event to Sponsor

An independent Medical Monitor will be appointed by the PI. The CHOP-based PI ([name]) and/or research coordinators will report SAEs that are both unexpected and probably or possibly related within 24 hours of becoming aware of the event, with a detailed completed report sent to the IRB and Medical Monitor within three working days of the event. The Medical Monitor will assess all SAEs. For each SAE that is both unexpected and probably or possibly related to study, [name] will provide sufficient medical history and clinical details for a safety assessment to be made with regard to continuation of the trial. The Medical Monitor will sign each SAE report after review. All SAE reports will be retained, and all SAE reports will be available for review by DSMB members and NICHD staff.

Event	Expected in pediatric ARDS	Serious adverse event	Pre-specified safety outcome
Death	Yes	Yes	Yes
Pneumothorax requiring chest tube	Yes	Yes	Yes
Other air leak not requiring chest tubes	Yes	Yes	Yes
Ventilator-associated pneumonia	Yes	Yes	Yes
New or progressive multiple organ dysfunction syndrome (increase in organ failure score or death 7 days after randomization)	Yes	Yes	Yes
Cardiac arrest	No	Yes	No
Arrhythmia	No	Yes	No
Hypotension	Yes	No	No
Need for extracorporeal membrane oxygenation	Yes	Yes	No

Need for renal replacement therapy	Yes	Yes	No
Brain herniation	No	Yes	No
New-onset seizures (without history of epilepsy)	No	No	No
Pulmonary embolus/deep vein thrombosis	No	Yes	No
Placement of new tracheostomy	Yes	Yes	No
Increase in vasopressor support due to acidosis	Yes	No	Yes
Protocol termination due to failure criteria	No	No	Yes

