#### **9.1.2 Blinding**

The intervention will not be blinded to clinicians or investigators. Blinding is not feasible for an intervention as fundamental and as clinically labile as ventilator management. To minimize selection bias that could occur due to pre-enrollment awareness of  $\Delta P$  assignment, randomization will occur only after informed consent and enrollment.

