The higher  $\Delta P$  strategy specifically could plausibly be associated with a relatively higher risk of pneumothorax requiring chest tube, other air leak not requiring chest tubes, or new or progressive multiple organ dysfunction syndrome (which has been associated with adults, but not children, with higher  $V_T$ ). To mitigate these risks, we reiterate the prescribed range of  $\Delta P$  and  $V_T$  within each arm of the trial and the ability to adjust. The higher  $\Delta P$  strategy could also shorten time on the ventilator, and plausibly decrease risk for ventilator-associated pneumonia; and have better gas exchange with less acidosis, thus improving hemodynamic stability and lowering risk for new or progressive multiple organ dysfunction syndrome.

The lower  $\Delta P$  strategy specifically could plausibly be associated higher rates of acidosis requiring additional vasopressor support, ventilator-associated pneumonia (via longer ventilation), and overall prolonged ventilation. To mitigate these risks, we again highlight the prescribed range of  $\Delta P$  and  $V_T$  within each arm of the trial to mitigate acidosis. The lower  $\Delta P$  strategy could also have lower rates of pneumothorax or other air leak, and if those complications were to sufficiently prolong ventilation, then the lower  $\Delta P$  strategy could actually shorten overall time on ventilation.

Finally, all risks that have been reported with (but not necessarily causally linked to) use of either high or low  $\Delta P$  listed above are consistent with the risks subjects could experience simply having a diagnosis of ARDS. Neither strategy is a priori anticipated to increase mortality.

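### Air leak is pre-specified only as two outcomes divided by an unblinded chest-tube decision, with no once-per-child count of all leaks

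*Protocol*

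**What the plan says.** Section 5.3 gives the list: "Secondary Safety Endpoints include: pneumothorax requiring chest tube; acidosis requiring additional vasopressor support; protocol termination for failure criteria; other air leak not requiring chest tubes". The synopsis (Safety Evaluations) names the same two air-leak items. The event table in 8.6 has a row for each, "Pneumothorax requiring chest tube" and "Other air leak not requiring chest tubes", both marked as expected, serious and pre-specified safety outcomes. No list contains an outcome for air leak of any kind.

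Section 9.4.2 allows that high ΔP may carry a "relatively higher risk of pneumothorax requiring chest tube, other air leak not requiring chest tubes"; as a third possible harm it adds multiple organ dysfunction that is new or progresses. For the other arm the same section does not divide the harm by chest tube: "The lower $\Delta P$ strategy could also have lower rates of pneumothorax or other air leak".

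On blinding, 9.1.2 states: "The intervention will not be blinded to clinicians or investigators". No section standardises when a chest tube is placed or provides blinded adjudication of air leak.

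On analysis, 6.3.3 summarises adverse events by type, body system, severity and relationship, with exact binomial 95% intervals. Under 8.3 all adverse events are recorded, and under 8.6 the DSMB reviews all of them. Section 4.4 sets no explicit stopping rules.

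**The concern.** The protocol reasons about air leak as one harm but measures it only in two parts. What separates the parts is a treatment decision, not the leak itself, and it is made by people who know the assigned pressure. If that decision differs by arm, children move between the two outcomes with no change in how many leak.

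Two further problems need no bias at all. The categories leave a gap and an overlap, so their counts cannot simply be added. And if air leak is infrequent, halving the event count in a trial of 160 weakens both comparisons. At stake is how clearly the DSMB, and the planners of the later trial that this one is meant to inform, can see a plausible harm of the high arm.

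**Working it through.** **The plan's own figure.** None is stated for air leak. The power figure in 6.4 concerns hypoxemia resolution and is not at issue.

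**Inputs.** From the protocol: 160 subjects (6.4) randomised 1:1 (9.1.1), so 80 per arm. Assumed, because the protocol gives neither: the leak rate p and the share of leaks that get a chest tube s, in each arm (H = high ΔP, L = low ΔP). For steps 1 to 3, every leak is taken to fall in exactly one category.

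**Step 1. Formulas.** Drained = p·s; undrained = p·(1 − s). The two arm differences add up to the total difference:

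[pH·sH − pL·sL] + [pH(1 − sH) − pL(1 − sL)] = pH − pL.

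Each half depends on s; the sum does not. If pH = pL, the halves move by equal amounts in opposite directions. If pH > pL, at least one half must be higher in the high arm.

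**Step 2. Precision loss with equal drainage.** Two yardsticks were used: (i) flat Beta(1,1) priors, flagging when the posterior probability of a higher rate in the high arm exceeds 0.90; (ii) a two-sided Fisher test at 0.05. Both were summed exactly over all binomial outcomes. The 0.90 threshold is borrowed from the efficacy calculation in 6.4.

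Take pH = 20%, pL = 10%, s = 50% in both arms. Each half expects 80 × 0.20 × 0.5 = 8 versus 80 × 0.10 × 0.5 = 4 events. All leaks: 80 × 0.20 = 16 versus 80 × 0.10 = 8.

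| Outcome | Expected, high v low | RR | Flag > 0.90 | Fisher |
|---|---|---|---|---|
| Each half | 8 v 4 | 2.0 | 45% | 14% |
| All leaks | 16 v 8 | 2.0 | 69% | 35% |

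At half these rates (10% versus 5%, s = 50%) the same method gives 27% per half against 45% for all leaks, and 4% against 14% by Fisher. All are low, but the total is better each time.

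**Step 3. Drainage that differs by arm.**

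| Assumed leak, high v low | Drained share, high v low | Drained half | Undrained half | All leaks |
|---|---|---|---|---|
| 20% v 10% | 30% v 60% | 4.8 v 4.8 (RR 1.00), flagged 9% | 11.2 v 3.2 (RR 3.50), flagged 84% | 16 v 8 (RR 2.00), flagged 69% |
| 10% v 10% | 70% v 40% | 5.6 v 3.2 (RR 1.75), flagged 29% | 2.4 v 4.8 (RR 0.50), flagged in the opposite direction 31% | 8 v 8 (RR 1.00), flagged 9.5% |

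With a small gap (10% leak in both arms, drained share 60% versus 50%), the drained half is flagged 14% of the time. By Fisher, the second row rejects about 6% of the time in each half.

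**Step 4. Do the categories cover air leak?**

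| Event | Counted as |
|---|---|
| Pneumothorax with chest tube | first outcome |
| Pneumothorax without chest tube | second outcome, if *other* is read to include it |
| Other leak without chest tube | second outcome |
| Other leak with chest tube | neither, read literally |
| Child with an event of each kind | both |

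Children with any leak = first + second − children in both + children whose only leak falls in neither. The last two terms cannot be read from the two listed outcomes.

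**The case against.** A reader might infer that either half can show or hide an arm difference whatever the true leak rate, so that harm from high ΔP could go unseen. The documents do not support that. Both halves are pre-specified and both are serious adverse events in 8.6, so they would be seen together. In the first row of step 3 the drained half shows nothing, but the undrained half is flagged 84% of the time, more often than the total. In the second row the false signal comes with an opposite shift in the other half, which is the visible mark of reclassification. The misleading picture arises only if one half is read alone, and nothing in the protocol tells anyone to do that.

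Other limits also stand:

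- The 0.90 flag is not a safety rule of this trial. Section 6.3.3 plans summaries with confidence intervals, and no decision is tied to either half.
- The leak rates and drainage shares are assumed, and nothing in the protocol shows that drainage would differ by arm.
- Air leak is not the sole named harm: 9.4.2 also names new or progressive multiple organ dysfunction, and its order of listing is not a ranking.
- Because all adverse events are recorded, a total could largely be rebuilt afterwards, and an analysis plan that is not shown may define one.
- Separating leaks that need a procedure from those that do not conveys severity.
- A total is not free of unblinded judgement, since finding small leaks depends on how hard clinicians look.

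These points limit the size of the concern but do not remove it. The endpoint lists in the protocol fix the split and its gap, the precision loss needs no bias, and a total chosen after results are known carries less weight than one named beforehand.

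**Conclusion.** The point holds as a modest, worthwhile improvement to the safety outcomes. That air leak is pre-specified only in two parts, divided by an unblinded treatment decision, is established from the text; that the parts do not cleanly partition it follows from reading their wording literally. The cost in precision is clear in direction. Its size, 45% against 69% on the posterior flag or 14% against 35% by Fisher, rests on assumed leak of 20% versus 10%, equal 50% drainage, 80 per arm and yardsticks the protocol does not set for safety. Bias from arm-dependent drainage is possible for one half read alone, but it is not shown to be likely and cannot conceal a true excess in both halves.

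**What to change.** In the synopsis, section 5.3 and the 8.6 table, add any new air leak, with or without chest tube, each child counted once, as a pre-specified safety outcome summarised and compared by arm. Keep the two existing categories as reported components. This sets no rule on when a chest tube is placed.

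The cost is one derived variable from adverse-event data already recorded, plus wording in three places. There are two downsides. The total mixes minor and major leaks, although the components still show severity. And detection of small leaks remains unblinded, so the total removes the effect of the drainage decision but not that of how closely clinicians look.

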## 8.4 Definition of a Serious Adverse Event (SAE)

An SAE is any adverse intervention experience occurring in relation to study procedures that results in any of the following outcomes:

- death,
- a life-threatening event (at risk of death at the time of the event),
- prolongation of existing hospitalization, or
- a persistent or significant disability/incapacity

Important medical events that may not result in death, be life-threatening, or require escalation of care may be considered a SAE when, based upon appropriate medical judgment, they may jeopardize the subject and may require medical or surgical intervention to prevent one of the outcomes listed in this definition.

A distinction should be drawn between serious and severe AEs. A severe AE is a major event of its type. A severe AE does not necessarily need to be considered serious. For example, nausea which persists for several hours may be considered severe nausea, but would not be an SAE. On the other hand, a stroke resulting in only limited disability may be considered a mild stroke, but would be an SAE.

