### **9.2 Data Collection and Management**

Detailed clinical data will be recorded, including demographics (age and sex), severity of illness (Pediatric Risk of Mortality [PRISM] IV; Pediatric Logistic Organ Dysfunction [PELOD] 2), co-morbidities (prematurity, immunocompromised status, stem cell transplant), and ARDS etiology (e.g., pneumonia, sepsis, trauma, aspiration). Pre- and post-randomization ventilator settings, oxygenation, ancillary therapy use, and adverse events will be documented daily until discontinuation of invasive ventilator support (i.e., extubation or removal of ventilator for subjects with tracheostomy). Organ failures (PELOD 2 score), vasopressor support, and clinical outcomes will be monitored until hospital discharge or 90 days, whichever is sooner. REDCap will serve as the data collection interface, and will require password-protected access.

Site investigators and research staff will be trained to collect data using electronic case report forms (CRFs). The CRF will be password-protected with safeguards to maintain confidentiality for all data entered into the CRF.

An electronic Manual of Operations (MOO) describing Standard Operating Procedures (SOP) for data collection will be prepared to ensure consistent documentation. The PICU research team will maintain an enrollment log that will link each potential subject to a unique study number. All data collection forms will contain this unique study number. Enrollment logs will be maintained by the PICU research team in a secure location accessible to study staff only. Identifiable information will be collected and stored locally, but no identifiable information will be transmitted to the Data Coordinating Center (DCC) at Penn. All data received at the DCC will be coded using a subject ID.

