#### **9.4.2 Risk Assessment**

The potential risks of this study are related to 1) potential exposure to less effective or less safe ΔP (above minimal risk with the potential for direct benefit), and 2) breach of confidentiality (not above minimal risk).

Potential risks associated with the ventilation protocol (e.g., hemodynamic instability, shock, cardiac dysrhythmias, pneumothorax, air leak, agitation, prolonged mechanical ventilation) are all part of the natural history of ARDS. Thus, all of these potential risks are associated with the ventilation protocols. These risks, and the steps enacted to protect against these risks, will be specified in the parent/legal guardian consent forms, all of which will be HIPAA-compliant.

Several people and organizations may have access to identifiable information. They will need this information to conduct the research, to assure the quality of the data, or to analyze the data. These groups include: members of the research team and other authorized staff at CHOP; people from agencies and organizations that perform independent accreditation and/or oversight of research such as the Department of Health and Human Services, Office for Human Research Protections, and the NIH who is sponsoring this research. The parent/legal guardian will be made aware of the requirement that the participant's deidentified data will be shared through NIH databases. These data will not include identifiers like their name, medical record number or date of birth. If the parent/legal guardian agrees, data including some identifiable information can be retained for the purposes of future research at CHOP. To gain access to this data, CHOP researchers must promise not to try to re-identify the participant. The parent/legal guardian can tell us during the consent conversation whether they will allow the participant's data to be shared in this way.

**Protection against Risks:** Study participation is voluntary. The parent/legal guardian(s) do not have to take part for their child to receive care at CHOP. If they decide not to take part or if they change their mind later, there will be no penalties or

loss of any benefits to which they were otherwise entitled. Additionally, the DSMB, Medical Monitor, and AE/SAE reporting plans will minimize risks of harm.

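### The only specifically circulatory safety outcome is a vasopressor increase attributed to acidosis, a judgment made knowing the arm; hypotension's fixed non-serious entry conflicts with the SAE definition

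*Protocol*

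**What the plan says.** Section 9.4.2 of the protocol opens its account of ventilation risks with "Potential risks associated with the ventilation protocol (e.g., hemodynamic instability, shock, cardiac dysrhythmias, pneumothorax, air leak, agitation, prolonged mechanical ventilation". These are stated for the ventilation protocol as a whole and described as part of the natural history of ARDS.

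Section 5.3 lists "acidosis requiring additional vasopressor support" as a safety endpoint. The synopsis carries the same item, and section 6.2 makes the section 5 safety endpoints secondary endpoints of the trial. The section 8.6 table has the matching row, "Increase in vasopressor support due to acidosis": expected, not an SAE, a pre-specified safety outcome.

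In the same table (columns: expected, SAE, safety outcome) the hypotension row reads "Hypotension Yes No No". Section 8.4 defines seriousness by consequence, for events in relation to study procedures, and includes "a life-threatening event (at risk of death at the time of the event".

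Section 9.4.2 assigns the acidosis pathway to the low ΔP arm, which it says might have "higher rates of acidosis requiring additional vasopressor support, ventilator-associated pneumonia (via longer ventilation), and overall prolonged ventilation". For the high arm it suggests less acidosis and better hemodynamic stability.

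**The concern.** A trial that names shock as a risk needs a circulatory safety measure that works equally well in both arms. This one counts an event only if somebody decides that acidosis caused it. Clinicians and investigators know the arm (sections 3.2 and 9.1.2), vasopressor use is left to the clinician (section 3.1.2), and the protocol itself leads them to expect acidosis in the low arm. The same clinical event could be labelled differently in the two arms. An increase in vasopressor for any other reason falls outside the outcome altogether.

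Two things are at stake. The first is whether a named secondary safety endpoint can be read as a fair comparison, including a test of the protocol's own suggestion that high ΔP may improve hemodynamic stability. The second is whether a life-threatening hypotensive episode is handled as an SAE. Section 8.6 has the Medical Monitor assess SAEs, and section 6.3.3 has SAEs described in detail; non-serious events receive neither.

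**Working it through.** There is no stated figure to reproduce, so the check sets the sections side by side.

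**1. Coverage in the section 8.6 table.** The table has 16 rows. Seven are pre-specified safety outcomes: death, pneumothorax with a chest tube, other air leak, ventilator-associated pneumonia, multiple organ dysfunction, vasopressor increase due to acidosis, and protocol termination for failure. The directly circulatory rows are:

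| Row | Expected | SAE | Safety outcome |
|---|---|---|---|
| Cardiac arrest | No | Yes | No |
| Arrhythmia | No | Yes | No |
| Hypotension | Yes | No | No |
| Vasopressor increase due to acidosis | Yes | No | Yes |

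So 1 of the 4 is a safety outcome, and it is restricted by cause. Two are SAEs only (for example "Cardiac arrest No Yes No"). Hypotension is neither. Shock has no row of its own.

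**2. What the restricted outcome measures.** Let p be the proportion of an arm with any vasopressor increase and a the share of those labelled as due to acidosis. The outcome estimates p × a in each arm, so the low-to-high ratio is

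(p_low × a_low) / (p_high × a_high).

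If any-cause rates are equal, p cancels and the ratio is a_low / a_high. That quantity mixes a real difference in acidosis with a difference in labelling, and the count alone cannot separate them. The any-cause ratio p_low / p_high does not contain a. The protocol gives neither p nor a, so no size can be attached.

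**3. Whether all-cause information is collected.** Yes. Section 9.2 says "vasopressor support, and clinical outcomes will be monitored until hospital discharge or 90 days, whichever is sooner", with no restriction by cause, and section 5.1.1 agrees.

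**4. Table against definition.** Section 8.4 asks what the event led to. The section 8.6 table answers by event type, with a fixed entry for hypotension, and no sentence says that the entry is a default or that section 8.4 prevails. For a life-threatening hypotensive event in relation to study procedures, the two give opposite answers.

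**The case against.** The strongest reply is that nothing goes unrecorded. All adverse events go on the case report form (section 8.3), are tabulated by type and body system with exact intervals for incidence (section 6.3.3), and are reviewed by the DSMB whether serious or not (section 8.6). Cardiac arrest and arrhythmia are SAEs, and multiple organ dysfunction is both an SAE and a safety outcome. This stands. A reader might infer that circulatory harm is not counted; the documents do not support that. What is missing is a pre-specified, cause-neutral outcome. Organ dysfunction does not supply it, because it is not specific to the circulation.

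A reader might also infer that the protocol names circulatory harm from high airway pressure and then leaves it out. It does not name it. Section 9.4.2 gives hemodynamic instability for the ventilation protocol generally, and its high-arm risks are pneumothorax, other air leak and organ dysfunction, all of them pre-specified. Section 3.4 notes higher mean airway pressure in the high arm but draws no circulatory consequence.

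Nor is the outcome biased by definition. It applies to both arms, and if low ΔP truly causes more acidosis, an acidosis outcome should show it. Any numerical inflation would only restate assumed attribution shares. What remains is that the comparison is open to differential attribution. An operational rule for attribution may sit in another document, and its absence here is not held against the protocol. Such a rule would make labelling more consistent, but escalation from other causes would stay outside the outcome.

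On seriousness, nothing says that the table overrides section 8.4, and the expedited route in section 8.6 requires an unexpected event, so expected hypotension would not trigger it anyway. It would be too strong to say that the Medical Monitor could never see such an event. The contradiction is real but can be settled in a sentence.

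**Conclusion.** The point holds in a limited form and should be corrected. The one specifically circulatory safety outcome depends on a causal label given with knowledge of the arm, along the pathway the protocol links to the low arm. Vasopressor escalation from other causes is not a pre-specified safety outcome, although it is captured as adverse-event data. The fixed SAE entry for hypotension contradicts section 8.4.

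The size is unknown: it depends on any-cause vasopressor rates and attribution shares that the protocol does not give. The count of 1 in 4 circulatory rows follows from the table and from treating those four rows as the directly circulatory ones. The primary endpoint is unaffected, and no stopping rule uses this count (section 4.4 provides no explicit rules).

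**What to change.** In the synopsis, section 5.3 and section 8.6, make the pre-specified safety outcome any increase in vasopressor support, whatever the cause, defined identically in both arms and derived from the vasopressor data already monitored. Keep attribution to acidosis as a reported breakdown.

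Count over a fixed window from randomization. The window should not be limited to time on the assigned protocol: section 4.3 ends that protocol when the primary outcome is reached, which is hypothesized to happen sooner with high ΔP, so the arms would have unequal time at risk. The 28 days used for the primary endpoint is one possible length.

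Add one sentence to section 8.6: the SAE column is a default, and any listed event that meets section 8.4, hypotension included, is reported as an SAE.

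The cost is mainly wording. An all-cause count includes shock unrelated to ventilation, which adds noise, though randomization balances it in expectation. Vasopressor decisions stay unblinded, so the new count depends less on judgment but is not free of it. The protocol does not say how finely vasopressor use is recorded, so the case report form must be checked, and extended if needed, so that an increase can be defined.
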